5.4 BREAKTHROUGH INFECTION ENDPOINTS

Table 9. Breakthrough infection endpoints

Breakthrough Infection Endpoint	Outcome	Timepoint#	Population measure	Comparison	Measure of association
i.	Breakthrough infection	To Day-28 visit;	Incidence risk	Fractional vs. Standard	Descriptive only
ii.	Breakthrough infection by time-	Month-6	Incidence risk	Fractional	Descriptive

	period (<14 days, Day 14 – Day-28	visit; and		vs. Standard	only
	visit, Day-28 visit – Month-6 visit,	Month-12			
	Month-6 visit – Month-12 visit)	visit			
iii.	Breakthrough infection by clinical		Incidence risk	Fractional	Descriptive
111.	spectrum (initial infection)*		incluence risk	vs. Standard	only
	Draulthrough infaction		Incidence rate	Fractional	Descriptive
iv.	Breakthrough infection		incidence rate	vs. Standard	only
	Breakthrough infection by clinical		Incidence rate	Fractional	Descriptive
v.	spectrum*		incidence rate	vs. Standard	only
:	Time to initial breakthrough		Survival Curve	Fractional	Descriptive
vi.	infection		Survival Curve	vs. Standard	only
	Time to initial breakthrough		Committee L Committee	Fractional	Descriptive
vii.	infection by clinical spectrum*		Survival Curve	vs. Standard	only

^{*}Categorised as Mild, Moderate, Severe, Critical as per Australian guidelines for the clinical care of people with COVID-19: https://app.magicapp.org/#/guideline/L4Q5An/section/nV2P3n "Analysis to be repeated at each analysis timepoint, for the risk and rate of breakthrough infection to that timepoint.

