6.18 ANALYSIS OF BREAKTHROUGH INFECTIONS

Table 15. Generic Estimand-to-Analysis table for all breakthrough infection endpoints for incidence risk (specified in Table 9).

(specified in Table 9).				
Primary Objective (as per Protocol): Identify any difference in the risk of clinically significant COVID-19 cases between any of the study groups [Indonesia Trial and BCOV22]; Evaluate the safety of the booster dose regimens [all studies]				
Estimand (for each trial vaccine):		Incidence risk of [OUTCOME]* to [TIMEPOINT]*, by dosage (fractional or standard) and trial vaccine in adults 18 years or older in Indonesia who have been primed through previous vaccination with one of the included primary series.		
ESTIMAND Attributes:		Incorporation of Estimand Attribute in ANALYSIS:		
Treatment Fractional dose (for each	trial vaccine)	Study arms Interventions (for each trial vaccine): Fractional dose Comparisons (for each trial vaccine): Standard dose		
Target population Adults 18 years or older in Indonesia/Mongolia who have been primed through previous vaccination with one of the included primary series.		Analysis set All randomised participants		
Variable		Outcome measure		
SARS-CoV-2 infection (bre		At least one positive SARS-CoV-2 test (PCR)		
Handling of intercurrent		Handling of missing data		
Receipt of 4 th dose (self-initiated)	Strategy ⁴ Treatment Policy (interpret results in conjunction with 4 th dose coverage)	Active surveillance for SARS-CoV-2 is not being done. Therefore, participants without a positive SARS-CoV-2 test will be included in the analysis under the assumption that they have not had a breakthrough infection.		
Receipt of 4 th dose (rescue) Treatment Policy (interpret results in conjunction with extent of rescue vaccination)				
Population-level summary measure		Analysis approach		
Incidence risk (proportion	n positive)	The incidence risk (a proportion) will be estimated in each group (arm [fractional or standard] and trial vaccine) with 95% CI using the proportion command in Stata. Analyses are descriptive only (no comparisons between arms will be made).		

^{*}This table is generic for all breakthrough infection endpoints for incidence risks (with varying combinations of outcomes & timepoints) specified in Table 9 as they will be analysed in the same way.

Table 16. Generic Estimand-to-Analysis table for all breakthrough infection endpoints for incidence rate (specified in Table 9).

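### SAP Table 9 row vii plans survival curves for first breakthrough infection by severity with no rule for first infections of another severity; read as Kaplan-Meier curves, they would overstate each severity's cumulative risk

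*SAP*

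**What the plan says.** SAP Section 5.4, Table 9, lists seven breakthrough infection endpoints. Four features bear on this point.

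- **Rows vi and vii.** Both concern "Time to initial breakthrough" infection and both have "Survival Curve" as the population measure. Row vii splits the endpoint: "infection by clinical spectrum".
- **Classes.** The footnote gives the split: "Categorised as Mild, Moderate, Severe, Critical as per Australian guidelines".
- **Row iii.** This is the matching risk endpoint. Severity there is that of the first infection: "spectrum (initial infection".
- **Status.** All rows are marked "Descriptive only".

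SAP Section 6.18 contains two analysis tables. Table 15 is headed "Generic Estimand-to-Analysis table for all breakthrough infection endpoints for incidence risk" and Table 16 "Generic Estimand-to-Analysis table for all breakthrough infection endpoints for incidence rate". Neither covers the survival curves. The only censoring rules are in Table 16. They censor at the last attended visit and at any positive test, with re-entry 28 days later and repeat infections counted. The rules on positive tests, re-entry and repeats suit a rate, not a time to first infection. The SAP does not mention competing events or cumulative incidence functions.

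**The concern.** Each participant can have only one first infection, and it belongs to one class. A mild first infection therefore makes a moderate, severe or critical first infection impossible for that person. A severity-specific survival curve needs a rule for that situation, and the SAP gives none.

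The default in survival software is to censor the person at the mild infection. That treats them as still able to have a first infection of the plotted class and spreads their remaining probability over the participants still at risk. One minus the curve is then no longer the proportion of the arm who have a first infection of that class. It is too large for every class, and the excess grows with the overall infection risk.

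At stake is a report in which the four severity curves do not add up to the overall curve beside them. The largest relative excess falls on the rarer classes, which in the mixes assumed below are the more serious ones.

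**Working it through.** **Inputs.** From the documents: four exclusive classes and a survival curve as the measure (SAP Table 9), 12 months of follow-up and 400 participants per arm in Mongolia (SAP Section 3.3). The documents give no infection risk, severity mix or expected event count, so there is no planned figure to reproduce. The overall 12-month risk F and the share q of first infections in each class are assumptions, shown over a range.

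**Formulas.** Assume constant hazards and no loss to follow-up. The total hazard is L = -ln(1-F), and a class with share q has hazard qL.

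- True cumulative incidence of the class: qF.
- One minus Kaplan-Meier, other classes censored: 1 - exp(-qL) = 1 - (1-F)^q.

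**Example.** For F = 30% and q = 7%, the true value is 0.07 × 0.30 = 2.10%. The Kaplan-Meier complement is 1 - 0.70^0.07 = 2.47%, which is 17% too high.

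**Range.** Each cell gives true value → Kaplan-Meier complement, in per cent.

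| Mix (mild/moderate/severe/critical) | F | Mild | Moderate | Severe | Sum of classes |
|---|---|---|---|---|---|
| 90/7/2/1 | 5 | 4.50 → 4.51 | 0.35 → 0.36 | 0.10 → 0.10 | 5.00 → 5.02 |
| 90/7/2/1 | 10 | 9.00 → 9.05 | 0.70 → 0.73 | 0.20 → 0.21 | 10.00 → 10.10 |
| 90/7/2/1 | 30 | 27.00 → 27.46 | 2.10 → 2.47 | 0.60 → 0.71 | 30.00 → 30.99 |
| 90/7/2/1 | 50 | 45.00 → 46.41 | 3.50 → 4.74 | 1.00 → 1.38 | 50.00 → 53.22 |
| 70/20/7/3 | 5 | 3.50 → 3.53 | 1.00 → 1.02 | 0.35 → 0.36 | 5.00 → 5.06 |
| 70/20/7/3 | 10 | 7.00 → 7.11 | 2.00 → 2.09 | 0.70 → 0.73 | 10.00 → 10.25 |
| 70/20/7/3 | 30 | 21.00 → 22.09 | 6.00 → 6.89 | 2.10 → 2.47 | 30.00 → 32.51 |
| 70/20/7/3 | 50 | 35.00 → 38.44 | 10.00 → 12.94 | 3.50 → 4.74 | 50.00 → 58.18 |

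- **Low risk (5-10%).** The largest excess in the sum is 10.25 - 10.00 = 0.25 points. On 400 participants that is 0.0025 × 400 = 1 person.
- **High risk (30-50%).** Across both mixes, the moderate, severe and critical classes are overstated by 15% to 19% at F = 30% and by 29% to 38% at F = 50%.
- **Limit.** As q becomes small, the ratio of the two quantities tends to -ln(1-F)/F: 1.05 at F = 10%, 1.19 at 30% and 1.39 at 50%. The relative excess therefore cannot go beyond about 40% in this range.

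**Simulation.** With 400 participants per arm, 500 replicates and the 90/7/2/1 mix, the Kaplan-Meier complements summed to 31.15% against an overall 30.15% (F = 30%), and to 53.08% against 49.92% (F = 50%). The cumulative incidences summed to the overall figure each time.

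**The case against.** **No estimator is named.** Row vii does not mention Kaplan-Meier. An analyst could keep people with a first infection of another class in the risk set to the end of follow-up as non-events. Without dropout, one minus that curve is the cumulative incidence. This stands: a reader might infer that the SAP commits itself to inflated curves, and it does not. It leaves the choice open, and the usual default is the one that inflates.

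**The risks are already reported correctly.** Row iii with Table 15 gives severity-specific risk as a simple proportion of all randomised participants. Someone with a mild first infection stays in the denominator for moderate disease, so there is no inflation. This also stands. It would be wrong to infer that the trial's severity-specific risks are overstated; the issue is confined to the curves.

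**The dose comparison.** A reader might infer that the curves would bias fractional against standard dose. The documents do not support that. Take two arms with the same moderate hazard (0.15) and severe hazard (0.01), and mild hazards of 0.40 and 0.70. The Kaplan-Meier complement for moderate disease is 1 - exp(-0.15) = 13.9% in both. The cumulative incidence is (0.15/0.56)(1 - exp(-0.56)) = 11.5% in one and (0.15/0.86)(1 - exp(-0.86)) = 10.1% in the other. The first reflects equal hazards and the second unequal absolute risks. They answer different questions, and the SAP does not say which one row vii is meant to answer.

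**The size may be negligible.** Table 15 says there is no active surveillance, so recorded risk may sit at the low end, where the excess is about one participant per arm at most. That cannot be settled from the documents.

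**Another reading of row vii.** If it meant the first infection of a given severity, counting reinfections, one class would not preclude another. The word *initial* in row vii, and the matching restriction in row iii, argue against this.

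**Conclusion.** The point holds as a minor one. Row vii asks for survival curves on competing events without naming an estimator or a rule for the competing class. Read in the usual way, one minus each curve overstates that severity's cumulative risk, and the parts exceed the whole.

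The direction is the same in every scenario examined. The size rests on assumed infection risk, severity mix and constant hazards: negligible at 5-10% overall risk, and material for the rarer classes at 30-50%.

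No test, primary endpoint or sample size depends on row vii. SAP Section 7.1 lists no survival-curve figure for breakthrough infection.

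**What to change.** - **Row vii.** Replace the survival curve with: *cumulative incidence function by severity (Aalen-Johansen), with first infection of another severity as a competing event*. Stacked, the four curves then sum to the overall incidence.
- **Row vi.** Keep the survival curve.
- **Both rows.** State the censoring rule, namely the last attended visit, and treat deaths the same way in both rows so that the parts still add up.
- **Row iii.** Add a note that its figures may still differ from the curves if there is dropout. Table 15 counts anyone without a positive test as uninfected, whereas any censoring-based curve, Aalen-Johansen included, removes people at their last visit.

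The cost is a line or two of SAP wording and a different plotting command. No new data are needed.

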6 STATISTICAL METHODOLOGY

6.1 GENERAL METHODOLOGY

6.1.1 Summary of changes compared to the protocols

- "Functional antibodies" have been described more precisely as "ACE2 binding inhibition by neutralising antibody" in the SAP.
- The SAP added to the definition of seroresponse a specification for participants with binding antibody levels under the limit of detection.
- The "interim analysis" described in the protocol is considered in the SAP as the final
 analysis of the Day-28 endpoints as the intention is to only conduct this analysis
 once all Day-28 data is available (no interim analyses are specified in the SAP).
- Grading for hardness and swelling in Mongolia will not consider interference with daily activities as per the protocol as this information is not being captured.
- The protocol does not specify blinding/unblinding of statisticians and data analysts (only specified for participants, those evaluating reactogenicity, vaccinator, immunologists and laboratory staff, clinical investigators); details on blinding of statisticians and data analysts are specified in this SAP.
- In the Mongolia trial protocol, warmth and itch are binary presence/absence variables, with presence falling under Grade 3 and 4 reactions; in the SAP, warmth and itch are to be analysed as binary presence/absence variables with no grading.
- The BCOV22 protocol specifies non-inferiority analyses in terms of seroresponse at Day-28 (from BCOV21), Month-6, and Month-12. The analysis of Day-28 binding antibody data from BCOV21 has already been conducted by the BCOV21 investigators, and this SAP does not specify re-analysis of this data. Further, Month-6 and Month-12 analyses specified in this SAP are based on the superiority framework and will use continuous data only (a binary seroresponse variable will not be considered).

6.1.2 Framework

The primary endpoint is testing for non-inferiority in seroresponse, with a non-inferiority margin of -10%. The secondary endpoints are testing for superiority. The reactogenicity and safety endpoints are descriptive and will be interpreted in conjunction with the results of the primary and secondary endpoints.

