Booster doses of Covid-19 vaccines are available to all adults in Mongolia and there may be no direct benefits for participants enrolling in this study, apart from the opportunity to learn their antibody response following the booster. In addition, the fractional dose booster may be shown to be equally effective with less reactogenicity. Participants will receive a heterologous boost which may be shown to be superior to a homologous boost. Studies have shown that mRNA boosting potentially offers superior immunogenicity for individuals primed with AstraZeneca.

While early reports from Israel and the US confirm the effectiveness of a first booster dose of Covid-19 vaccine in some heterologous or homologous regimens, there is only limited data on the use of fractional dosage in heterologous regimens. This study will provide data crucial to designing optimal vaccine strategies in Mongolia and other countries that have used Sinopharm (*BBIBP-CorV®*), AstraZeneca (ChAdOx1-S, or *Vaxzevria®*) or Sputnik V (Gam-COVID-Vac) as primary two dose regimens.

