3. TRIAL OBJECTIVES AND OUTCOMES

3.1 Objectives

3.1.1 Primary objectives

- To assess and compare the immune response measured as binding antibodies (IgG ELISA) following standard versus fractional doses of Pfizer vaccine given as a single additional dose to adults 18 years or older in Mongolia who have been primed through previous vaccination with Sinopharm, AstraZeneca or Sputnik vaccines. (Timepoint – 28 days post vaccination)
- To assess the rate and severity of reactogenicity within one-week post-booster for each schedule evaluated.

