4.2 Justification for dose

This project is designed to evaluate the potential use of fractional dose and heterologous booster regimens for individuals who have previously received two doses of Covid-19 vaccine. The fractional dose has advantages for the individual and the broad community. At an individual level, the likelihood of moderate adverse reactions is reduced by the use of a fractional dose. Existing data suggests that immunogenicity and effectiveness will be maintained, but this will be evaluated early in the project and if immunogenicity proves to be inadequate this will be addressed according to the recommendations of the DSMB. At a national and global level, the approach carries the potential to greatly expand the availability of Covid-19 vaccine, helping to correct the inequity that currently characterises the global Covid-19 situation.

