5.1.2 Reactogenicity within 7 days of boosting

Reactogenicity will be measured using a standardised daily questionnaire (diary card) that elicits the presence and severity (mild, moderate, severe, life-threatening [grades 1-4, respectively]), or absence, of local reactions (pain, tenderness, redness, hardness, swelling, necrosis, warmth, or itch at or near the injection site) or systemic reactions (fever, nausea, vomiting, diarrhoea, headache, fatigue/malaise, myalgia, arthralgia, or enlarged lymph nodes) within the last 24 hours on days 1 through 7. Warmth and itch will be recorded as presence/absence only (i.e., not graded). The primary endpoint for reactogenicity will be solicited grade 3 or 4 local or systemic reactions within 7 days of vaccination, inclusive.

Table 6. Primary endpoints

Primary Endpoint	Outcome	Timepoint	Population measure	Comparison	Measure of association
i.	Seroresponse (see Table 5)	Day-28 visit	% (95% CI)	Fractional vs. Standard	Difference in %
ii.	Reactogenicity: solicited grade 3 or 4 local or systemic reactions within 7 days of vaccination, inclusive	7 days post- booster	% (95% CI)	NA (descriptive)	NA (descriptive)

All analyses will be conducted separately for the different booster vaccines, amongst all strata combined, and then stratified by the primary series strata (see

Strategy for multiple imputation

Protocol Numbers:

81803 (V9), 81800 (V4), BCOV22 (V3)

Statistical Analysis Plan

Page 22 of 52

Multiple imputation will be done using a multivariate imputation model (MICE) and 50 imputations. Covariates in the imputation model will be the same as those specified for imputation under the hypothetical strategy (Section 6.15.1 Implementation of the Hypothetical Strategy). For the binary seroresponse outcome, binding antibody levels will be imputed (rather than the relative increase from baseline or binary seroresponse), and then seroresponse will be derived using the imputed value/s.

Subgroup analyses and tests for interaction).

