6.1.8 Reporting

Clinical Study Reports are to be produced for the funder, separately for each trial (Indonesia Trial, BCOV22 Observational Study, and Mongolia Trial). All analyses will be conducted according to the SAP. However, the formatting of figures and tables may be modified, and additional descriptive (but not comparative) statistics provided, to comply with the ICH E3 Guidelines on the Structure and Content of Clinical Study Reports.¹

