Incidence risk (proportion	n) of at least one solicited emic reaction within 7 days	Proportions will be estimated with 95% Clopper-Pearson binomial confidence intervals using the Ci Stata command.	
		Supplementary analysis: The following reaction-specific descriptive analyses will also be conducted: Number and percentage of individuals with each reaction type, presented in a radial graph (Dummy Figure 3). Number and percentage of participants with each reaction type, by severity grade (Dummy Figure S 3). Distribution of the day of onset for each reaction type Distribution of the duration of each reaction type	

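### Grade 3–4 reactogenicity is a listed primary endpoint of a randomised, blinded dose comparison, but the SAP pre-specifies no between-arm estimate: a missed estimate that is cheap to add

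*SAP*

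**What the plan says.** **Objective and sizing.** Protocol 3.1.1 asks for immunogenicity to be both assessed and compared between doses. The reactogenicity objective is worded differently: "To assess the rate and severity of reactogenicity within one-week post-booster for each schedule evaluated". Protocol 11.1 sizes reactogenicity by the width of a single group's interval, and Protocol 11.3 has the data shown separately by group and time point.

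**Endpoint.** SAP 5.1.2: "The primary endpoint for reactogenicity will be solicited grade 3 or 4 local or systemic reactions within 7 days of vaccination, inclusive". Table 6 lists this as primary endpoint ii and marks both its comparison and its measure of association as not applicable, descriptive.

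**Analysis.** Table 11 (SAP 6.13) names the fractional dose as intervention and the standard dose as comparison, but the planned estimator is per arm: "Proportions will be estimated with 95% Clopper-Pearson binomial confidence intervals using the Ci Stata command". Supplementary output covers counts by reaction and grade, day of onset and duration. No risk difference, ratio or test appears. SAP 6.1.2 gives the general rule: "The reactogenicity and safety endpoints are descriptive and will be interpreted in conjunction with the results of the primary and secondary endpoints".

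**Reporting.** SAP 6.1.8 lets the study reports depart from the SAP in formatting, with "additional descriptive (but not comparative) statistics provided".

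**Why the dose contrast is of interest.** Among possible benefits, Protocol 2.4 says "the fractional dose booster may be shown to be equally effective with less reactogenicity". Protocol 4.2, arguing for the dose, says "the likelihood of moderate adverse reactions is reduced by the use of a fractional dose".

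**The concern.** Whether the half dose causes fewer reactions is a between-dose question. The design can answer it: dose is randomised 1:1 within strata, with 400 planned per arm (SAP 3.3), and participants and reactogenicity assessors are blinded throughout the 7-day window (to day 28 in Protocol 4.1 and SAP 3.5; for one week in the protocol synopsis). The plan stops short of the estimate.

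The reader will be given an immunogenicity difference with its confidence interval and asked to weigh it against two unlinked reaction percentages. The natural next step is to see whether the two intervals overlap, which is a poor way to read a randomised contrast: it understates the precision of the difference. Even the unsolicited adverse-event and breakthrough-infection endpoints (SAP Tables 8 and 9) name fractional versus standard as the comparison, although descriptively. The primary reactogenicity endpoint does not.

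**Working it through.** **Inputs.** Group sizes of 200 and 100 and a 50% rate for any local or systemic reaction (Protocol 11.1); 400 per dose arm (SAP 3.3); two-sided 95% intervals (SAP 6.1.3). The documents give neither a grade 3–4 rate nor a target difference, so every rate below other than 50% is an assumption.

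**1. The plan's own figures.** The half-width for a single proportion is 1.96 × √(p(1−p)/n).
- n = 200, p = 0.5: 1.96 × √(0.25/200) = 6.9 points.
- n = 100, p = 0.5: 1.96 × √(0.25/100) = 9.8 points.

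Both match Protocol 11.1. The Clopper-Pearson interval that the SAP will use is slightly wider, at 7.1 and 10.2 points. These are single-group figures and do not show how precisely the two doses can be compared.

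**2. Precision of the dose contrast.** The approximate (Wald) half-width for fractional minus standard, with a common rate p and n per arm, is 1.96 × √(2p(1−p)/n). For example, p = 0.10 and n = 400 gives 1.96 × √(0.18/400) = 4.2 points.

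| Rate | 400 per arm | 200 per arm | 100 per arm |
|---|---|---|---|
| 50% (Protocol 11.1, any reaction) | 6.9 | 9.8 | 13.9 |
| 30% (assumed) | 6.4 | 9.0 | 12.7 |
| 10% (assumed) | 4.2 | 5.9 | 8.3 |
| 5% (assumed) | 3.0 | 4.3 | 6.0 |
| 2% (assumed) | 1.9 | 2.7 | 3.9 |

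The 400 column is the pooled comparison. The 200 and 100 columns apply within the Sinopharm stratum and within the AstraZeneca or Sputnik strata.

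**3. What is lost by comparing two separate intervals.** At 50% with 400 per arm, each arm's Wald half-width is 1.96 × √(0.25/400) = 4.9 points. The two intervals separate only when the observed rates differ by about 2 × 4.9 = 9.8 points, whereas the interval for the difference excludes zero from about √2 × 4.9 = 6.9 points.

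**4. A hypothetical example.** Take 40/400 (10.0%) on standard dose and 24/400 (6.0%) on fractional dose.
- Clopper-Pearson intervals: 7.2% to 13.4% and 3.9% to 8.8%. They overlap.
- Wilson limits for the same counts: 7.43% to 13.33% and 4.06% to 8.77%.
- Newcombe score interval for the difference of −4.0 points:
  - lower limit: −4.0 − √((6.0 − 4.06)² + (13.33 − 10.0)²) = −7.9;
  - upper limit: −4.0 + √((8.77 − 6.0)² + (10.0 − 7.43)²) = −0.2.

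The interval for the difference excludes zero although the two single-arm intervals overlap.

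**The case against.** The strongest reply is that the SAP does what the protocol asks. The objective is per schedule and omits the comparison that the immunogenicity objective names; the sizing is single-group; and the protocol presents the data by group. The descriptive choice is explicit, and safety and breakthrough infection are handled descriptively too. This stands: there is no contradiction between the documents and no mistake in the analysis.

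A reader might nonetheless infer three stronger things that the documents do not support.
- *That reactogenicity is co-primary in the sense of a success criterion.* Table 6 lists it as primary, but SAP 6.1.2 reserves the test for seroresponse, and the decision rule in SAP 2.3 does not involve reactogenicity.
- *That the trial claims lower reactogenicity and cannot support it.* Protocol 2.4 offers it as a possibility, and Protocol 4.2 gives a rationale written before any trial data. Counts with known denominators will be reported for each arm, so anyone can compute a crude difference and its interval. What is missing is pre-specification.
- *That SAP 6.1.8 forbids a comparison.* It limits what may be added when study reports are written. It does not prevent a SAP revision, and SAP 3.5 describes how revisions to comparative analyses are to be made.

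A further objection is that the interval may say little if grade 3–4 reactions are rare. At 400 per arm (two-sided 5%), power would be 46% for 5% versus 2.5% and 21% for 2% versus 1%, all assumed rates. This stands as a caution. It is a reason to report estimation without a test, because an interval shows the imprecision openly.

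Finally, Table 11 analyses participants by vaccine received and counts missing diary values as no reaction, so a difference from that set is not automatically a clean randomised contrast. This also stands, and the fix has to address it.

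**Conclusion.** The point holds as a cheap improvement. A listed primary endpoint in a randomised, blinded dose comparison has no pre-specified between-dose estimate, and one cannot be added at the study-report stage under SAP 6.1.8 without revising the SAP. The plan is consistent with the protocol, so this is a missed estimate and not an error.

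The available precision with 400 per arm is roughly ±3.0, ±4.2 or ±6.4 points at rates of 5%, 10% or 30%. Those figures rest on assumed rates, a common rate in both arms, full planned enrolment and a Wald approximation; a score interval will differ somewhat. Whether such precision is useful depends on a difference of interest that the documents do not state.

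There is also a gap in severity. The primary endpoint starts at grade 3, while the rationale in Protocol 4.2 concerns moderate reactions, which are grade 2 in Protocol Table 1. A contrast on grade 3–4 alone would not address that rationale.

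**What to change.** **Change.**
- In SAP Table 6 (row ii) and Table 11, add the risk difference, fractional minus standard, with a 95% score-based interval. Protocol 11.3 already names this family of intervals for seroresponse.
- As a supplementary measure, add the same quantity for any graded solicited reaction of grade 2 or higher. Exclude warmth and itch, which the SAP leaves ungraded, and note that hardness and swelling in Mongolia are graded without interference with activity (SAP 6.1.1).
- Label both as estimation only, with no hypothesis test, and add a matching clause to SAP 6.1.2.
- Report the difference by randomised arm if any doses received differ from allocation.
- State beside it that missing diary values are counted as no reaction. Table 11 already plans to describe missing values by study group.

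If the team prefers no contrast, the alternative is to state that no conclusion of lower reactogenicity will be drawn.

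**Cost.** No new data, and little text or code. Because the SAP also covers the Indonesia Trial, the edits to Tables 6 and 11 must be worded to fit both trials. The grade 2 or higher measure is not yet a defined endpoint and needs a short definition. The downside is one or two further intervals that need cautious reading and may be inconclusive if grade 3–4 events are rare.
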